3.6. DRUGS NOT PERMITTED DURING THE CLINICAL TRIAL

While in the clinical trial, this protocol does not permit the use of the following drugs and/or changes in medication:

- Loop diuretics.
- SGLT2 inhibitors.
- Pioglitazone

If the attending physician considers that for the best care of the patient the use of any of the above mentioned drugs or changes in treatment is absolutely essential, the patient will be withdrawn from the study, the blinding for the patient will be broken and the promotor informed.

Any other change in medication which does not lead to withdrawal from the study will be recorded in the CRD.

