3.5. DRUG UNDER EVALUATION. BLINDING AND RELABELLING OF THE MEDICATION

The investigational medicinal product (IMP) is dapagliflozin 10 mg given once daily (film coated tablets, oral use).

The comparator will be placebo matching dapagliflozin 10 mg.

Either dapagliflozin or placebo will be administered through out the planned intervention period of the study (12 weeks).

AstraZeneca will donate both dapagliflozin 10 mg and placebo resembling dapagliflozin 10 mg for the study.

Identity of investigational product(s)

Investigational product	Dosage form and strength	Manufacturer
Dapagliflozin	10 mg, Green, plain, diamond shaped, film coated tablet (orally)	AstraZeneca
Matching placebo for dapagliflozin	Green, plain, diamond shaped, film coated tablet (orally). Does not contain active ingredient	AstraZeneca

Primary packaging of the Investigational Medicinal product (IMP) will be carried out by AstraZeneca or their designee in accordance with Good Manufacturing Practice (GMP).

Unlabeled bottles (identical) containing 35 tablets of each IMP will be provided by AstraZeneca.

The tablets contain lactose, which may cause discomfort in lactose-intolerant individuals.

Label, storage and distribution are a promotor's responsibility.

Preparation and labelling of Investigational Medicinal Product

To allow for adequate treatment for the diabetes, only participants will be blinded to the treatment they receive. Attending physicians will know the group in which every patient is. To preserve blinding for the patient, the study medication (active and placebo) will be sent from AstraZeneca to a certified company (LogistaPharma), where, in coordination with the CRO of the study [ODDS, S.L.], it will be counted, labeled and distributed to the participating centers. The IMPs will be labelled in accordance with Good Manufacturing Practice (GMP) and local regulatory guidelines for labeling. The labels will fulfill GMP Annex 13 requirements for labelling.

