3.7. INTERACTIONS WITH OTHER MEDICINAL PRODUCTS AND OTHER FORMS OF INTERACTION

The summary of the product characteristics details the interactions of dapagliflozin as follows:

Pharmacodynamic interactions

Diuretics

Dapagliflozin may add to the diuretic effect of thiazide and loop diuretics and may increase the risk of dehydration and hypotension.

Insulin and insulin secretagogues

Insulin and insulin secretagogues, such as sulphonylureas, cause hypoglycaemia. Therefore, a lower dose of insulin or an insulin secretagogue may be required to reduce the risk of hypoglycaemia when used in combination with dapagliflozin.

Pharmacokinetic interactions

The metabolism of dapagliflozin is primarily via glucuronide conjugation mediated by UDP glucuronosyltransferase 1A9 (UGT1A9).

In *in vitro* studies, dapagliflozin neither inhibited cytochrome P450 (CYP) 1A2, CYP2A6, CYP2B6, CYP2C8, CYP2C9, CYP2C19, CYP2D6, CYP3A4, nor induced CYP1A2, CYP2B6 or CYP3A4. Therefore, dapagliflozin is not expected to alter the metabolic clearance of coadministered medicinal products that are metabolised by these enzymes.

Effect of other medicinal products on dapagliflozin

Interaction studies conducted in healthy subjects, using mainly a single dose design, suggest that the pharmacokinetics of dapagliflozin are not altered by metformin,

pioglitazone, sitagliptin, glimepiride, voglibose, hydrochlorothiazide, bumetanide, valsartan, or simvastatin.

Following coadministration of dapagliflozin with rifampicin (an inducer of various active transporters and drug-metabolising enzymes) a 22% decrease in dapagliflozin systemic exposure (AUC) was observed, but with no clinically meaningful effect on 24-hour urinary glucose excretion. No dose adjustment is recommended. A clinically relevant effect with other inducers (e.g. carbamazepine, phenytoin, phenobarbital) is not expected.

Following coadministration of dapagliflozin with mefenamic acid (an inhibitor of UGT1A9), a 55% increase in dapagliflozin systemic exposure was seen, but with no clinically meaningful effect on 24-hour urinary glucose excretion. No dose adjustment is recommended.

Effect of dapagliflozin on other medicinal products

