3.8. END POINTS

Primary: Changes in mean nocturnal BP from baseline (week 0) to last visit (week 12).

Secondary:

- Changes in office BP from baseline (week 0) to last visit (week 12).
- Changes in HbA1C from baseline (week 0) to last visit (week 12).
- Changes in albuminuria from baseline (week 0) to last visit (week 12).
- Natural variability of mean nocturnal BP on separate visits (placebo group).

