3.10. WITHDRAWAL OF PATIENTS FROM THE STUDY AND UNBLINDING

Any patient can be withdrawn from the study at anytime during follow-up based on medical criteria of attending physician. The latter will detail the reasons of the withdrawal and communicate it urgently to the coordinating office of the trial if needed. If the reason for withdrawal is an adverse event (AE), the patient will be followed according to the procedures described for AEs (3.16).

Any patient can decide to abandon the study at any time during the study.

Withdrawal from the trial for any reason is definitive. When leaving the study, the main reason will be recorded and, if possible, the patient should have a final exam with the content of the visit of week 12. Patients that abandon the study will not be substituted.

All the above mentioned situations cause unblinding of the study. The primary care physician is always aware of the medication that receives the patient (single blind) and

will be the contact person and responsible to break the blind. Contact details are available in the patient information form. After unblinding, the responsible primary care physician will report it to the coordinating office of the project (ODDS, S.L., [contact]).

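### Section 3.6 does not make clear which background medication changes mean withdrawal and which are only recorded, and section 3.13 has no analysis for changes made after randomisation by physicians who know the arm

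*Combined protocol and SAP*

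**What the plan says.** Three sentences of section 3.6 bear on the point.

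- The opening says that "this protocol does not permit the use of the following drugs and/or changes in medication". The list that follows holds three drug classes and no change.
- The second says that if the attending physician considers that "the use of any of the above mentioned drugs or changes in treatment is absolutely essential, the patient will be withdrawn from the study". The patient is then also unblinded.
- The last says: "Any other change in medication which does not lead to withdrawal from the study will be recorded in the CRD".

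Other sections set the context.

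- **Who knows the arm.** Section 3.5 states: "Attending physicians will know the group in which every patient is". The reason given is "To allow for adequate treatment for the diabetes, only participants will be blinded to the treatment they receive".
- **Foreseen changes.** Section 3.7 notes that "a lower dose of insulin or an insulin secretagogue may be required to reduce the risk of hypoglycaemia" with dapagliflozin.
- **Discretionary withdrawal.** Section 3.10 states: "Any patient can be withdrawn from the study at anytime during follow-up based on medical criteria of attending physician".
- **Population and visits.** Section 3.2 requires office BP above 140/70 mmHg at entry. The table in 3.20 has office BP at visit 0 and weeks 4, 8 and 12, and ABPM only at visit 0 and week 12.
- **Endpoint and analysis.** The primary endpoint in 3.8 is the change in nocturnal BP from week 0 to week 12. Section 3.13 uses t-tests in patients who complete three months, with regression for confounders if needed, and compares non-completers with adherers.

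**The concern.** Antihypertensive treatment acts directly on the primary outcome, and glucose-lowering treatment acts on HbA1c, a secondary outcome. The people who decide on these treatments know the allocation and see office BP twice between baseline and week 12. Changes can therefore differ between arms for reasons that include knowledge of the arm.

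Section 3.6 leaves room for two site practices. One site may keep a patient whose antihypertensive is raised at week 4, and the week-12 value then carries that drug's effect. Another may treat the same event as a change requiring withdrawal, and the patient drops out of the completers set. Section 3.13 examines neither path. At stake are the size and the interpretation of the primary contrast, and also the secondary endpoint on the natural variability of nocturnal BP in the placebo group, which would include any treatment changes.

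**Working it through.** **1. The text of 3.6, read two ways.**

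- *Narrow reading.* The words pointing to the list govern both nouns, so only the three classes lead to withdrawal and every other change is recorded. This is coherent, and it fits 3.5 and 3.7, where adjustment of diabetes treatment is foreseen. Antihypertensives other than loop diuretics may then be started or increased, with a record only.
- *Broad reading.* A change in medication is itself a ground for withdrawal. This sits badly with the section's last sentence and with 3.5 and 3.7.

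On either reading the last sentence is circular: a change is only recorded if it does not lead to withdrawal, but 3.6 does not say which changes do.

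**2. The analysis plan.** The regression in 3.13 is tied to the check of comparability between randomised groups. It does not address treatment started after randomisation. The comparison of non-completers with adherers describes the loss but does not correct for it.

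**3. The plan's own sample size (3.11).** Inputs: two-sided alpha 0.05, power 80%, difference 5 mmHg, SD 12 mmHg, allocation 2:1, drop-out 9%.

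- Placebo completers: (1.960 + 0.842)² × 12² × (1 + 1/2) / 5² = 67.8, so 68; active 136; total 204.
- Divided by 0.91 and rounded up: 75, 150 and 225. The stated figures reproduce.
- Expected completers: 150 × 0.91 = 136.5, about 137; 75 × 0.91 = 68.25, about 68. SE = 12 × √(1/137 + 1/68) = 1.78 mmHg. Power at 5 mmHg by the noncentral t is 79.8%.

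**4. If patients stay.** The documents give neither the frequency of antihypertensive changes nor their effect, so both are assumptions. Let q be the excess proportion intensified on placebo and e the effect in mmHg, fully present at week 12. The expected difference becomes 5 − q × e. Power uses the same SE:

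| q | e (mmHg) | Difference (mmHg) | Power |
|---|---|---|---|
| 0 | – | 5.00 | 79.8% |
| 5% | 5 | 4.75 | 75.7% |
| 15% | 5 | 4.25 | 66% |
| 15% | 10 | 3.50 | 49.9% |

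An excess in the active arm would reverse the sign of q and widen the difference.

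**5. If patients are withdrawn.** With total loss d, SE = 12 × √(1/(75(1−d)) + 1/(150(1−d))), and power is about Φ(5/SE − 1.96). For d = 15%, 20% and 30%, SE is 1.84, 1.90 and 2.03, and power is 78%, 75% and 69%, against 80% at the planned 9%. This counts lost numbers only. Selection that depends on arm comes on top, and a larger sample would not remove it.

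**The case against.** Four objections deserve an answer.

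- **A reader might infer that 3.6 flatly contradicts itself.** The documents do not support that. The narrow reading is coherent, and the limiting clause in the last sentence can be tied to the discretionary withdrawal in 3.10. The section is ambiguous and incomplete, and differing practice between sites is possible but not shown.
- **A comparison regardless of background changes is a legitimate target** for a drug added to usual care. This stands: keeping such patients does not in itself spoil the contrast. The gap is that 3.13 does not say this is the intended effect, and offers nothing to show how far changes made with knowledge of the arm contribute to it.
- **A reader might infer that the drug effect will be understated.** More intensification on placebo is plausible and would shrink the difference, but the documents contain no rate, and physicians who know the arm could act either way.
- **The 50% figure uses an added-drug effect of 10 mmHg**, twice the 5 mmHg that 3.11 takes for dapagliflozin. This also stands, so the figure belongs in a range whose mild end is 76%.

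The CRFs are in Annex I, which was not available here, so class, dose and date may already be captured.

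**Conclusion.** The concern holds as an unclear rule combined with a missing analysis. Section 3.6 does not separate changes that lead to withdrawal from changes that are only recorded, and 3.13 has no provision for antihypertensive or glucose-lowering changes after randomisation, although the physicians making them know the arm. Both outcomes, staying or being withdrawn, can bias the arm comparison.

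The size cannot be fixed from the documents. If the excess is on placebo, power falls from about 80% to between 76% and 50% over the three assumed cases. These rest on SD 12 mmHg, 137 and 68 completers, a true difference of 5 mmHg, and assumed values for q and e. The planned sample size itself is not in dispute. The point should be addressed before the analysis is fixed.

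**What to change.** 1. **Section 3.6.** The sponsor should reconcile the three sentences into one rule that every site applies. The clinical content of that rule is for the sponsor to decide.
2. **CRF.** Ensure that class, dose change and date are captured for the antihypertensive and glucose-lowering changes that are already to be recorded.
3. **Section 3.13, main analysis.** Report these changes by arm. State that patients with a recorded change stay in the main comparison regardless of it.
4. **Withdrawn patients.** Obtain the week-12 ABPM where possible. Section 3.10 already asks for a final examination with week-12 content on leaving, but 3.13 must admit such values for them to be of use.
5. **One prespecified sensitivity analysis.** Set week-12 nocturnal BP to missing after an antihypertensive start or increase, and multiply impute it from baseline ABPM and office BP. Treat HbA1c likewise after glucose-lowering changes.
6. **Placebo variability endpoint.** Report it with the number of placebo patients who had an antihypertensive change. Do not restrict it to patients without a change: that selects on a post-randomisation event linked to BP and would tend to understate variability.

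The cost is protocol wording, at most one structured CRF page, one table by arm and one extra analysis. The downside is that the imputation rests on an untestable assumption and on limited data, since ABPM is done only at visit 0 and week 12.

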3.7. INTERACTIONS WITH OTHER MEDICINAL PRODUCTS AND OTHER FORMS OF INTERACTION

The summary of the product characteristics details the interactions of dapagliflozin as follows:

Pharmacodynamic interactions

Diuretics

Dapagliflozin may add to the diuretic effect of thiazide and loop diuretics and may increase the risk of dehydration and hypotension.

Insulin and insulin secretagogues

Insulin and insulin secretagogues, such as sulphonylureas, cause hypoglycaemia. Therefore, a lower dose of insulin or an insulin secretagogue may be required to reduce the risk of hypoglycaemia when used in combination with dapagliflozin.

Pharmacokinetic interactions

The metabolism of dapagliflozin is primarily via glucuronide conjugation mediated by UDP glucuronosyltransferase 1A9 (UGT1A9).

In *in vitro* studies, dapagliflozin neither inhibited cytochrome P450 (CYP) 1A2, CYP2A6, CYP2B6, CYP2C8, CYP2C9, CYP2C19, CYP2D6, CYP3A4, nor induced CYP1A2, CYP2B6 or CYP3A4. Therefore, dapagliflozin is not expected to alter the metabolic clearance of coadministered medicinal products that are metabolised by these enzymes.

Effect of other medicinal products on dapagliflozin

Interaction studies conducted in healthy subjects, using mainly a single dose design, suggest that the pharmacokinetics of dapagliflozin are not altered by metformin,

pioglitazone, sitagliptin, glimepiride, voglibose, hydrochlorothiazide, bumetanide, valsartan, or simvastatin.

Following coadministration of dapagliflozin with rifampicin (an inducer of various active transporters and drug-metabolising enzymes) a 22% decrease in dapagliflozin systemic exposure (AUC) was observed, but with no clinically meaningful effect on 24-hour urinary glucose excretion. No dose adjustment is recommended. A clinically relevant effect with other inducers (e.g. carbamazepine, phenytoin, phenobarbital) is not expected.

Following coadministration of dapagliflozin with mefenamic acid (an inhibitor of UGT1A9), a 55% increase in dapagliflozin systemic exposure was seen, but with no clinically meaningful effect on 24-hour urinary glucose excretion. No dose adjustment is recommended.

Effect of dapagliflozin on other medicinal products

In interaction studies conducted in healthy subjects, using mainly a single-dose design, dapagliflozin did not alter the pharmacokinetics of metformin, pioglitazone, sitagliptin, glimepiride, hydrochlorothiazide, bumetanide, valsartan, digoxin (a P-gp substrate) or warfarin (S-warfarin, a CYP2C9 substrate), or the anticoagulatory effects of warfarin as measured by INR. Combination of a single dose of dapagliflozin 20 mg and simvastatin (a CYP3A4 substrate) resulted in a 19% increase in AUC of simvastatin and 31% increase in AUC of simvastatin acid. The increase in simvastatin and simvastatin acid exposures are not considered clinically relevant.

Other interactions

The effects of smoking, diet, herbal products and alcohol use on the pharmacokinetics of dapagliflozin have not been studied.

Paediatric population

Interaction studies have only been performed in adults.

Population of advanced age (65-75 years old)

Population older than 65 years of age are more likely to have a mildly reduced glomerular filtration rate (eGFR 60-90 mL/min $\times 1.73m^2$) and/or being on treatment with drugs that may affect renal function (as ACE inhibitors or Angiotensin-2 receptor blockers). In these patients, as in the usual clinical practice, administration of dapagliflozin should be done with extra caution (education of the patient and self monitoring of symptoms).

Specific drug alert

Severe cases of diabetic ketoacidosis associated with treatment with canagliflozin, dapagliflozin and empagliflozin have been reported. It is recommended to health professionals:

- Perform monitoring of ketone bodies in patients who develop symptoms suggestive of diabetic ketoacidosis during treatment even when blood glucose levels do not suggest diagnosis.
- Inform patients in treatment about the symptoms of diabetic ketoacidosis and the need to see the doctor if they occur.

3.8. END POINTS

Primary: Changes in mean nocturnal BP from baseline (week 0) to last visit (week 12).

Secondary:

- Changes in office BP from baseline (week 0) to last visit (week 12).
- Changes in HbA1C from baseline (week 0) to last visit (week 12).
- Changes in albuminuria from baseline (week 0) to last visit (week 12).
- Natural variability of mean nocturnal BP on separate visits (placebo group).

3.9. VISITS, VARIABLES AND MEASUREMENTS

Four clinical visits are planned in every patient at 0 (recruitment and randomization), 4, 8 and 12 weeks. Information on personal and family history of disease, clinical examination (including office BP determination), ABPM and blood and urine samples will be obtained on visits 0. The variables measured in the blood and urine samples depend on the criterium of the attending physician. For this trial, only HbA1c, serum creatinine, estimated glomerular filtration rate (eGFR) and albuminuria are mandatory. All this information, except personal and family history of disease, will also be collected at week 12 (see “3.20. Conduct of the study”). Thirty days after the end of the medication (visit of week 12) all participants will be contacted by telephone to assess safety. For the initial laboratory data required in the CRF, data obtained in primary care in the previous 3 months could be valid. These data will be repeated at the end of the study. Informed consents for the study will be signed by the patients before coming to the hospital. Blood samples extractions included in this protocol will be done, handled and analyzed at each clinical setting according to usual clinical

practice. No blood sample storage will be needed in this study. Extra blood samples drawn will be handled as described in “3.23. Addendum”.

The relationship of the procedures performed at every clinical visit is presented below (see “3.20. Conduct of the study”). Case report forms (CRFs) are presented in Annex I. Albuminuria will be measured according to generally used and previously described methodologies(18-23).

ABPM will be measured using Mobil-o-Graph that will give us 24 hours brachial and central BP as well as pulse wave velocity and heart rate(24). As diary of activity of the patient will not be recorded, in this study, nocturnal (or nighttime) blood pressure refers to measurements within the period from 12.00 p.m. to 6.00 a.m.

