3.13. PLAN OF ANALYSIS

The main analysis will compare baseline and final visit values of nocturnal blood pressure and all the rest of quantitative variables of interest within each stratum of albuminuria by means of paired t-test. Changes of nighttime blood pressure from baseline to final visit among patients with high and very high albuminuria levels will be compared to placebo with t-test.

Variables will be described by means of mean (and standard deviation) or proportion depending on the type of variable considered. Whenever the test of hypothesis may involve discrete variables, chi-squared test will be used.

Comparability of treatment and placebo groups will be tested (t-student or chi-squared test, depending on the variable) to assess randomization, and linear regression will be used to adjust for potential confounders, if needed; stratum of albuminuria at randomization will be forced in the model.

To respond to secondary objectives, the same analyses will be done for each stratum of albuminuria at randomization.

Only patients that complete the 3-month follow-up will be analyzed. Patients who do not complete the follow-up will be compared to those who adhere to the protocol.

No interim analysis is planned. A *p* value<0.05 will be considered as statistically significant.

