3.20. CONDUCT OF THE STUDY

The table below shows the plan of visits for every patient participating in the study and

the procedures to be done at every visit and where it takes place.

	Visit 0 (recruitment&randomization)		Visit Week 4 (±3 days)	Visit Week 8 (±3 days)	Visit Week 12 (final visit)	Phone Call (30 days after the final visit)
	Primary care	Hospital (within 7 days from primary care visit)	Primary care	Primary care	Hospital	Hospital
Verification of inclusion and exclusion criteria and obtention of informed consent	✓					
Randomization and drug distribution for the entire follow-up		✓				
Personal and family history	✓					
Office BP	✓		✓	✓	✓	
Pill counting			✓	✓	✓	
Clinical exam	✓		✓	✓	✓	
Blood sample (to confirm entry criteria; recent [previous three months] analyses are acceptable) and urine	✓	✓ ^(*)			✓	
ABPM		✓			✓	
Adverse events monitoring			✓	✓	✓	✓

(*)

Only necessary if not all measurements in the blood sample drawn in primary are available

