3.23. ADDENDUM

Patients included in this study will be part of an ongoing project financed for the period 2018-2020 by the “Fondo de Investigaciones Sanitarias (Instituto de Salud Carlos III), Referencia: PI17/01193” approved by the ethics committee of Hospital 12 de Octubre with the title “Papel de la presión arterial nocturna en la estratificación del riesgo cardiovascular: nuevas estrategias clínicas y experimentales” and aimed to evaluate oxidative stress, vascular remodeling and proteomic profiles in different clinical situations. To this end, coinciding with the blood extractions done in the hospital in this protocol (visits 0 and week-12), extra blood samples will be obtained, prepared and stored. Four blood tubes (7 ml/each) will be drawn, centrifuged and the plasma separated and stored in a private collection at Hospital 12 de Octubre ([name]). This information is included in the information for the patient sheet.

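### The week-0 baseline for HbA1c and albuminuria may be the entry-qualifying result, up to 3 months old, which distorts the planned within-stratum paired tests of these secondary endpoints

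*Combined protocol and SAP*

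**What the plan says.** Section 3.8 lists as secondary endpoints "Changes in HbA1C from baseline (week 0) to last visit (week 12") and "Changes in albuminuria from baseline (week 0) to last visit (week 12").

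Section 3.9 has blood and urine taken at visit 0 and says that "only HbA1c, serum creatinine, estimated glomerular filtration rate (eGFR) and albuminuria are mandatory". It then relaxes the timing of the initial laboratory values entered in the CRF: "data obtained in primary care in the previous 3 months could be valid". The same data are to be obtained again at the end of the study, so the older result becomes the comparator for week 12.

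The visit table in section 3.20 describes the primary care sample as serving "to confirm entry criteria; recent [previous three months] analyses are acceptable". Its footnote makes the hospital visit-0 sample necessary only when primary care measurements are incomplete. Section 3.23 reads differently: "coinciding with the blood extractions done in the hospital in this protocol (visits 0 and week-12), extra blood samples will be obtained".

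Section 3.13 compares baseline with final values of nocturnal blood pressure and "all the rest of quantitative variables of interest within each stratum of albuminuria by means of paired t-test". No section defines a laboratory baseline separate from the qualifying value or requires a repeat at randomization.

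**The concern.** Two things can go wrong when an eligibility result doubles as the endpoint baseline.

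- **Interval.** The change no longer covers the 12 treatment weeks alone. It also takes in whatever happened between the old sample and randomization.
- **Selection.** Patients enter because HbA1c was 7.5-10% and albuminuria was at least 30 mg/g (section 3.2), and they are placed in a stratum by whether albuminuria exceeded 300 mg/g (section 3.4). A later measurement tends back toward the population mean even if nothing is done.

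A paired t-test within a stratum cannot separate either effect from a treatment effect. Section 3.13 names nighttime blood pressure alone in its explicit comparison with placebo, so for HbA1c and albuminuria the paired test is the most clearly stated analysis. Secondary objective 3 also reports these variables by albuminuria subgroup, where the artefact would be unequal.

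**Working it through.** **1. The plan's own figure.** Section 3.11 gives a 5 mmHg difference, SD 12, two-sided alpha 0.05, 80% power, 2:1 allocation and 9% drop-out.

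- Placebo n = (1.960 + 0.842)² × 12² × (1 + 1/2) / 5² = 67.8, so 68; active 136.
- Divided by 0.91: 75 and 150, total 225, as stated.

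This rests on nocturnal blood pressure, with ABPM done at hospital visit 0 (section 3.20). The laboratory baseline does not enter it. The documents give no SD or power for HbA1c or albuminuria.

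**2. Interval.** Three months is about 13 weeks. 13 + 12 = 25 weeks, of which 13/25 = 52% is before treatment. Adding the 7 days allowed between the primary care and hospital visits gives 26 weeks and 14/26 = 54%. These are maxima.

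**3. Regression to the mean, no true change.** Expected shift = −(1 − r) × (mean of selected patients − population mean), where r is the correlation between qualifying and final value. All distributions below are assumptions; r runs from 0.6 to 0.9.

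| Variable | Assumed population | Selected mean | r | Shift |
|---|---|---|---|---|
| HbA1c | mean 7.0, SD 1.2 | 8.26 | 0.6 | −0.4 × 1.26 = −0.50 |
| HbA1c | mean 7.5, SD 1.2 | 8.38 | 0.7 | −0.3 × 0.88 = −0.26 |
| HbA1c | mean 8.0, SD 1.2 | 8.52 | 0.9 | −0.1 × 0.52 = −0.05 |
| Albuminuria 30-3000 | median 15, log-SD 1.5 | geometric 79.5 | 0.6 | (15/79.5)^0.4 − 1 = −49% |
| Albuminuria 30-3000 | median 60, log-SD 1.5 | geometric 129.5 | 0.9 | (60/129.5)^0.1 − 1 = −7% |

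**4. By albuminuria stratum.** With median 60, log-SD 1.5 and r = 0.8:

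- 30-300 mg/g (geometric mean 87.3): (60/87.3)^0.2 − 1 = −7%.
- Above 300 mg/g (geometric mean 604): (60/604)^0.2 − 1 = −37%.

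With median 60-100, between-patient log-SD 1.2 and within-patient log-SD 0.3-0.5, the upper stratum falls 10-28% and the lower moves between −5% and +1%. The fall is always larger above 300 mg/g. It is nearly confined to that stratum only if the population median lies well inside 30-300. With median 15 and r = 0.8, the lower stratum (geometric mean 69.0) also falls: (15/69.0)^0.2 − 1 = −26%.

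The 7-49% range in step 3 lets the strata occur in their natural proportions. The equal strata planned in section 3.4 would put more weight on the steeper one.

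**5. Effect on the tests, HbA1c.** Assume mean 7.5, SD 1.2, and correlations of 0.8 (qualifying to visit 0), 0.8 (visit 0 to week 12) and 0.7 (qualifying to week 12). Placebo has no true change; active has an assumed effect of −0.5.

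| | Qualifying value as baseline | Fresh visit-0 value as baseline |
|---|---|---|
| Mean placebo change | −0.27 | −0.09 |
| SD of change | 0.88 | 0.75 |
| Placebo paired test rejects, n = 34 | about 40% | 10% |
| Placebo paired test rejects, n = 68 | 69% | 16% |
| Active minus placebo | −0.50 | −0.50 |

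Here n = 34 is one placebo stratum after drop-out (37 × 0.91 = 33.7) and n = 68 is the whole placebo arm. The residual −0.09 is −(0.8 − 0.7) × 0.88. The SD of change rises by 0.88/0.75 − 1 = 17% in this selected population. In an unselected one, a drop in r from 0.8 to 0.7 gives √(0.3/0.2) − 1 = 22%.

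**The case against.** The strongest reply is that randomization protects the comparison that matters. The qualifying value predates allocation, so lag and regression to the mean fall on both arms alike in expectation. That stands, and step 5 shows it. A reader might infer that the estimated effect of dapagliflozin on HbA1c or albuminuria is biased; the documents do not support that. Section 3.13 also allows regression adjustment and repeats its analyses by stratum for the secondary objectives, so a between-arm analysis can be read into it, although the sentence on comparison with placebo names only nighttime blood pressure.

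Four further limits stand.

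- The permission is optional, so the share of patients with an old baseline is unknown.
- The regression figures contain no time term. A sample taken the day before would give the same result at the same correlation. They measure reuse of the qualifying value; pre-treatment drift is not quantified.
- A reader might infer from section 3.23 that week-0 values are available at no cost. Those tubes are blood only, and their plasma is stored for a separately financed project. The section 3.20 footnote makes the hospital laboratory sample conditional. Neither provides a clinical aliquot or a urine sample.
- In section 3.20 the three-month allowance is attached to the blood sample, and its reach to urine is unclear. Section 3.9 covers all initial laboratory data in the CRF, and albuminuria is among the mandatory items.

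None of this removes the mismatch between section 3.8 and sections 3.9 and 3.20.

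**Conclusion.** The point holds for the secondary endpoints HbA1c and albuminuria, and for eGFR as a collected variable. Their baseline is defined inconsistently, and as written it may be an older, selected value. The within-stratum paired tests would then tend to show improvement in both arms without any treatment effect, and the between-arm comparison would lose some precision.

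The size is uncertain because every distribution and correlation used is an assumption. The plausible range of spurious fall is about 0.05 to 0.5 points for HbA1c and about 7 to 49% for geometric mean albuminuria, greater above 300 mg/g. A larger fall in the very-high stratum could be misread as a stronger treatment effect there.

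The primary endpoint, the sample size and the expected difference between arms are untouched. This is a worthwhile and cheap correction, not a threat to the trial's main conclusion.

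**What to change.** - **Baseline.** Use results from the previous 3 months for eligibility and stratum only. Define the endpoint baseline as HbA1c, creatinine/eGFR and urine albumin/creatinine from blood and spot urine collected at hospital visit 0, before the first dose and not used for entry.
- **Text.** Reconcile section 3.9, the section 3.20 table and footnote, and section 3.23, so that this sample is mandatory and distinct from the stored research tubes.
- **Analysis.** In section 3.13, base conclusions on the between-arm comparison adjusted for that baseline and for albuminuria stratum, with albuminuria on the log scale. Keep within-arm changes as description. This is needed as well, because a fresh sample removes most but not all of the regression to the mean (0.09 of 0.27 points remains in the illustration).

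The cost is about 225 sets of routine assays, with one added clinical tube and a spot urine per patient, at a visit that already exists. The collection must be prospective, since a week-0 urine not taken cannot be recovered. Because the earlier result would still set the stratum, the change does not cure stratum misclassification and should not be credited with doing so.
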